11.5 Study Monitoring

The Investigator/regional Principal Investigator will allocate adequate time for remote study monitoring activities. The regional Investigator will also ensure that the Study Monitor, or

other compliance or quality assurance reviewer, is given access to all study-related documents and study related facilities.

The Study Monitor will review ICFs and eCRFs and compare them with source documents to verify adherence to the protocol, and to ensure complete, accurate, consistent, and timely collection of data. The Investigator will be asked to provide any missing information or to clarify any discrepancies found by the Study Monitor.

In addition to source document verification of CRFs and ICFs, the Study Monitor will review the Clinical Site Regulatory Binder that is to be maintained by the Principal Investigator.

Refer to the Study Monitoring Plan for source data verification (SDV) and remote monitoring requirements and frequency.

11.6 Case Report Forms and Study Records

All eCRFs will be completed according to eCRF completion guidelines. The Principal Investigator must electronically sign and date a declaration on the eCRF attesting to his/her responsibility for the quality of all data recorded and that the data represent a complete and accurate record of each participant's participation in the study. An electronic copy of the completed eCRF will then be sent to the Investigator to be retained for their records.

11.7 Data Monitoring Committee

The DMC will review participant safety data regularly (meeting at least biannually), and after 1,000 participants have completed 5 weeks of Follow-Up. The composition and policies of the DMC are described in the DMC Charter. If any safety concerns arise, these data will be conveyed to the DMC expeditiously. After review of the data, the DMC will make any recommendations regarding study conduct.

11.8 Protocol Violations/Deviations

Except for a change intended to eliminate an immediate hazard to a study participant, the protocol shall be conducted as described without any changes or deviations. Any change must be reported immediately to the Sponsor and to the IRB/EC and/or regulatory authority as required by guidelines or regulation.

11.9 Access to Source Documentation

Source documents provide evidence for the existence of the participant and substantiate the integrity of the data collected. Source documents including web-based documentation are to be filed at the regional centers.

Data reported entered in the eCRF that are transcribed from source documents must be consistent with the source documents or the discrepancies must be explained. The Investigator may need to request previous medical records or transfer records, depending on the study. Also, current medical records must be available for all data collected in the eCRF.

Refer to the Monitoring Plan for SDV review and requirements.

11.10 Principal Investigator Sign-Off on Electronic Case Report Forms

Whomever completes the medical assessment and initial consent for the participant is responsible for reviewing and signing off on the eCRF at the end of the study.

11.11 Data Generation and Analysis

All participant data relating to the study will be recorded directly into the eCRFs.

The Investigator must maintain accurate documentation (source data) that supports the information entered in the eCRFs.

The Investigator must permit study-related monitoring, audits, IRB/IEC review, and regulatory agency inspections and provide direct access to source data documents.

Monitoring details describing strategy (eg, risk-based initiatives in operations and quality such as Risk Management and Mitigation Strategies and Analytical Risk-Based Monitoring), methods, responsibilities and requirements, including handling of noncompliance issues and remote monitoring techniques are provided in the Monitoring Plan.

11.12 Retention of Data

Records and documents, including signed ICFs, pertaining to the conduct of this study must be retained subject to applicable local regulations after study completion, eg, in Canada 25 years. No records may be destroyed during the retention period without the written approval of the Sponsor. No records may be transferred to another location or party without written notification to the Sponsor.

11.13 Financial Disclosure

Investigators and sub-Investigators will provide the Sponsor with sufficient, accurate financial information as requested to allow the Sponsor to submit complete and accurate financial certification or disclosure statements to the appropriate regulatory authorities, e.g. US regulation 21 CFR Part 54, which also covers the spouse and each dependent child of the Investigator. Investigators are responsible for providing information on financial interests during the course of the study and for 1 year after completion of the study.

11.14 Publication and Disclosure Policy

The results of this study may be published or presented at scientific meetings. If this is foreseen, the Investigator agrees to submit all manuscripts or abstracts to the Sponsor before submission. This allows the Sponsor to protect proprietary information and to provide comments.

The Sponsor will comply with the requirements for publication of study results. In accordance with standard editorial and ethical practice, the Sponsor will generally support

publication of multicenter studies only in their entirety and not as individual site data. In this case, a coordinating Investigator will be designated by mutual agreement.

Authorship will be determined by mutual agreement and in line with International Committee of Medical Journal Editors (ICMJE) authorship requirements.

The Sponsor will adhere to the trials registration policy adopted by the ICMJE member journal. This policy requires that all clinical trials be registered in a public trials registry such as ClinicalTrials.gov, which is Sponsored by the National Library of Medicine.

13 APPENDICES

Appendix 1 Schedule of Events

Table 4 Schedule of Events

	Screening a Baseline	Daily on TX	Early TX Day	Last Tx Day	Post-Tx Follow-up		
Assessments			Phone Assessment 1	Phone Assessment 2	Phone Assessment 3	ET	
Visit Type (per specific country regulatory legislation)	Remotely or On-Site	Remotely	Remotely	Remotely	Remotely or On-Site	Remotely or On-Site	
Study Day	-7 to 1	1-35 ^d	7+3	28 +2	End of Study 35±3		
Participant Informed Consent (Virtual, if applicable/respective country) b	X						
Demographics (Virtual, if applicable/respective country)	X						
Medical History (Virtual, if applicable/respective country)	X						
Clinical Exam including Vitals (Virtual, if applicable/respective country)	X				X	X	
Pregnancy Test (Urine) ^c	X				X	X	
Concomitant Medications ^d	X	X	X	X	X	X	
Randomization	X						
Study treatment instructions ^e	X		X				
COVID related symptom assessment ^f			X	X	X	X	
NONS Self Administration ^g		X	X	X			
Questionnaire (online/paper) h		Xi	X	X	X	X	
Adverse Events		X	X	X	X	X	
Study Drug Accountability/Compliance		X	X	X		X	
Report if tested positive for COVID-19 infection		X	X	X	X	X	
Report need for Hospitalization/ER Visit for COVID-19 related sequelae		X	X	X	X	X	

Abbreviations: ER=emergency room; ET= early termination; NONS= nitric oxide nasal spray; Tx=treatment.

NONS (nitric oxide nasal spray)
Clinical Trial Protocol: COVID-NONS-04

- ^a Screening and baseline are to be taken within 7 days but may be taken at the same assessment. Post-Treatment Follow-up visits (end of study and ET) may be performed remotely. For countries requiring an in-person visit, these will be performed on-site, unless the participant is hospitalized, in quarantine or unable to visit the site for any reasonable cause as per the investigators' judgement; these visits may then be performed remotely and will not be considered a protocol deviation. Follow-up of all adverse events must be completed as described in the protocol Section 7.
- Participants will be asked to designate an emergency contact who will also sign informed consent. In the event the participant is hospitalized and cannot complete their treatment diary or questionnaire emergency contacts will be encouraged to provide symptoms on behalf of a participant in a COVID-19 symptoms list Diary (Appendix 2).
- ^c Pregnancy test to be self-reported if remote visit is allowed per respective country regulatory legislation; however, results must be confirmed at Screening prior to enrolling the participant on the study.
- d Excludes naturopathic products.
- For remote visits per respective country regulatory legislation, instructions on administering the study treatment will be provided via videocall on Day 1 and a check in call to confirm comfort with administration of the study treatment. For in-person visits, instructions will be given by the sites' staff with a confirmation of the participants' comfort with administration of the study treatment.
- Assessment for COVID-19 symptoms will be performed using the COVID-19 symptoms list (Appendix 2; Appendix 3).
- g Dosing should start within 2 days of the baseline assessment.
- For the Spray Bottle Use Perception Questionnaire PRO, participants will only provide their feedback on the usage of the spray bottle on Day 1 and Day 5 (Appendix 3).

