- 8. Participants who have any other condition that, in the opinion of the Investigator, would interfere with a participant's ability to adhere to the protocol (eg, participants whom are mentally or neurologically disabled and whom are considered not fit to their participation in the study), interfere with assessment of the investigational product, or compromise the safety of the participant or the quality of the data.

Planned Number of Participants: 13,000 to be randomized with a maximum of 11,480 participants initiating study treatment.

Test Product, Dose, and Mode of Administration: The test product is nitric oxide (NO) releasing solution delivered in the form of a nasal spray which will be self-administered three (3) times per day, morning, noon, and night for 28 days.

The comparator is a placebo of saline solution to be self-administered as the test product.

Duration of Treatment: Participants will be on study for 5 weeks (to include 1 week of screening/baseline, 4 weeks of treatment, 1 week of Follow-Up).

Efficacy Assessments: Participants will self-assess COVID-19-related symptoms, report if they have tested positive for COVID-19, and report if they need hospitalization or an ER visit. A positive COVID-19 test can be either by antigen or SARS-CoV-2 RT-PCR.

Safety Assessments: Adverse events (AEs) and discontinuations of treatment will be collected, and the number of participants that are hospitalized or visit the ED or ER for COVID-19/flu-like symptoms.

Study Endpoints: Primary Endpoint: Confirmed positive COVID-19 test (Both antigen and SARS-CoV-2 RT-PCR are acceptable) by Day 28.

Secondary Endpoint: Hospitalization or ER/ED visits for COVID-19/flu-like symptoms by Day 28.

Safety Endpoint: AEs and discontinuation of treatment.

Statistical Methods:

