2.2 Secondary Objectives and Endpoints

Objective	Endpoint	
To assess the efficacy of NONS in prevention of severe COVID-19	Hospitalization or ER/ED visits for COVID-19/flu-like symptoms by Day 28	
Assess tolerability of NONS in participants with all participants including those with COVID-19	AEs and discontinuation of treatment	

Abbreviations: AE=adverse events; ER/ED=emergency room, emergency department NONS=nitric oxide nasal spray.

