3 INVESTIGATIONAL PLAN

3.1 Overall Study Design and Plan

This is a multicenter, randomized, double-blinded, placebo controlled, Phase 3 clinical efficacy study evaluating NONS in healthy adult volunteers as a prevention treatment for individuals at risk from COVID-19 infection.

Up to 13,000 adult participants aged 18 or over with no known history of SARS-CoV-2 infection will be randomized into one of two cohorts of this study in a ratio of 1:1 (Treatment: Placebo Control). Participants with or without underlying medical conditions will be eligible to enroll. The NONS formulation proposed for use in this COVID-19 clinical study will be self-administered at a maximum of 3 times per day, morning, noon, and night for 28 days. Participants will be on study for 4 weeks of treatment (to include 5 days of Screening, 1 week of Follow-Up, participants will be followed for a total of approximately 5 weeks) as a viricidal Investigational Medical Product.

Participants will self-administer a nasal spray containing either blinded study treatment or placebo (herein called study treatment). Nitric oxide nasal spray (NONS) will be delivered from manual pump nasal spray container with 25 mL of solution with each nasal spray dispensing approximately 130-150 μ L of solution. After the subject blows their nose, each treatment will require two sprays per nostril, or about 0.5 mL per treatment.

The primary endpoint is to assess the efficacy of NONS in the prevention of COVID-19 infection as determined by a positive COVID-19 test (antigen or reverse-transcriptase polymerase chain reaction [RT-PCR]),

The secondary endpoints are to determine the proportion for participants requiring hospitalization or emergency room (ER/emergency department [ED]) visits for COVID-19 or flu-like symptoms by Day 28 and assess the safety and tolerability of use of NONS in participants with COVID-19.

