6.6 Efficacy Assessments

Participants will self-assess COVID-19-related symptoms (Section 6.6.2), report if they have tested positive for COVID-19, and report if they need hospitalization or an ER/ED visit as described in the Schedule of Events (Table 4). A positive COVID-19 test can be either by antigen or SARS-CoV-2 RT-PCR.

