6.6.2 In-Person On-Site/Telephone Contact

Study staff for sites requiring on-site visits will contact participants via telephone on Day 7 and 28 (all others performing remote monitoring will contact participants on Day 7, 28, and 35) as described in the Schedule of Events (Table 4) and confirm participants' current health status including presence of any COVID-19 symptoms (Appendix 2; Appendix 3), in addition to any ER or hospital visits that might have occurred as a result of COVID-19. Participants will also be asked about any challenges with administration or any AEs they may have experienced.

Participants who are hospitalized for any reason and are unable to attend their on-site visit / telehealth assessment or complete their daily diary should have their emergency contact notify study staff as soon as possible. Participants that are hospitalized for COVID-19 only are considered treatment failures. Participants that are hospitalized for any other reason may stay on the study at the discretion of the Investigator.

Follow-up visits (end of study and early termination assessments) will be performed preferably on-site (in countries where remote only conduct is not allowed), but if the participant is hospitalized, in quarantine or unable to visit the site in-person for any reasonable cause as per investigators' judgement, these visits may be performed remotely and will not be considered a protocol deviation. Follow-up of all adverse events must be completed as described in the protocol Section 7.

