9.5.2 Secondary Efficacy Analysis

For the secondary objective of prevention of medical intervention for COVID-19, the secondary endpoint will be executed similarly to the primary efficacy analysis above.

Participants who are hospitalized for COVID-19-related symptoms, but who test negative for COVID-19 will not be considered to have met the endpoint. The time of the endpoint will be considered the study day at which the participant was hospitalized or the day at which the ER/ED visit occurred even if a COVID-19 positive result was obtained before or after the day of the event.

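### The protocol's visit items are limited to COVID-19 while the secondary endpoint also covers flu-like symptoms, so capture of some ER/ED visits without admission is not assured

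*Combined protocol and SAP*

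**What the plan says.** **Endpoint.** Section 2.2 gives the secondary endpoint as "Hospitalization or ER/ED visits for COVID-19/flu-like symptoms by Day 28". Section 3.1 and the synopsis define it in the same way, so flu-like symptoms count as well as COVID-19.

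**Visit items.** Table 4 in Appendix 1 has one row for visits, marked for the daily reports, the three phone assessments and early termination: "Report need for Hospitalization/ER Visit for COVID-19 related sequelae". Section 6.6.2 has staff confirm health status at the scheduled contacts, "in addition to any ER or hospital visits that might have occurred as a result of COVID-19". Neither item mentions flu-like symptoms.

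**Wider wording elsewhere.** Under efficacy assessments, the synopsis says participants "report if they need hospitalization or an ER visit", with no limit on the reason. Section 6.6 is similarly general but refers to Table 4 for the detail. Under safety assessments, the synopsis lists as data to be collected "the number of participants that are hospitalized or visit the ED or ER for COVID-19/flu-like symptoms".

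**Analysis rule.** Section 9.5.2 states: "Participants who are hospitalized for COVID-19-related symptoms, but who test negative for COVID-19 will not be considered to have met the endpoint". It dates the event to the day of admission or of the ER/ED visit, whether a positive result came before or after that day.

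**The concern.** The endpoint and the items that should supply it do not have the same scope. Someone who goes to an emergency department with a feverish illness, is not admitted, and does not think it is COVID-19 may have an endpoint event under Section 2.2. Answering the Table 4 and Section 6.6.2 items literally, that person would not report it. Table 4 schedules no SARS-CoV-2 test, only a report of a positive one, so a participant may have no result to guide the attribution.

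This matters in two ways. First, visits are lost from a sparse endpoint. If the loss is equal in both arms it costs information more than it biases the comparison. If attribution is influenced by a test result or by a guess at the assigned spray, it need not be equal. Second, the quantity being estimated becomes unclear. With flu-like visits of any cause included, it is an effect on emergency care for respiratory illness. Filtered through participant attribution, it becomes an unspecified mixture of that and an effect on COVID-19 care.

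**Working it through.** The plan gives no event rate, sample size or power for this endpoint, so there is no figure of its own to reproduce. The check is mainly a comparison of texts.

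**1. Each kind of visit, followed through the plan**

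| Visit | Route into the data | Status under 9.5.2 |
|---|---|---|
| Admission, any attribution | SAE whatever the cause (7.1, 7.4.1) | Does not count if test-negative |
| ER/ED only, attributed to COVID-19 | Table 4 row and 6.6.2 contact | Counts if test-positive; test-negative or untested not addressed |
| ER/ED only, not attributed, positive test before or after | No dedicated item; AE or general-health reports only | Counts, dated to the visit |
| ER/ED only, flu-like, not attributed, negative or untested | No dedicated item; AE or general-health reports only | Within the 2.2 wording; not addressed in 9.5.2 |

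The gap lies in the last two rows. In the third row the analysis rule and the collection items conflict directly: the rule expects visits that precede a positive result, when the participant has least reason to call the illness COVID-19. A later contact could recover such a visit if the participant then links the two, but the plan does not ask for a look back. In the fourth row it is unclear whether the visit is an event at all.

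**2. Whether the other routes record a visit.** An ER/ED visit without admission is not in itself an SAE criterion in Section 7.1, although an important medical event may qualify. The AE fields in Section 7.7 are description, duration, severity, outcome, treatment and relationship; none is a visit or its date. Appendix 3 describes daily questions on dosing, adverse events, medication changes, general health changes and symptoms, and shows no visit question. An illness can therefore be recorded without the visit that would make it an endpoint.

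**3. How sparse the endpoint could be.** Section 9.2 expects 2 + 10 = 12 infections. With 5,740 per arm, daily hazard h = 0.000075 (placebo) or 0.15 × 0.000075 (NONS), and loss m = 0.0105 per day, expected events per arm are

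5,740 × h/(h + m) × (1 − exp(−28(h + m))),

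which gives 10.4 for placebo and 1.6 for NONS, 12.0 in all, in agreement with the plan. If Section 9.5.2 is read as requiring a positive test, secondary events come only from these infected participants.

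**4. What one event is worth.** Section 9.5.1 uses score-based inference and Section 9.5.2 follows it. With 1:1 allocation, equal risk sets, and all d events in one arm, each event contributes expectation 1/2 and variance 1/4, so z = (d − d/2)/√(d/4) = √d.

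- 3 v 0: z = 1.73, p = 0.083
- 4 v 0: z = 2.00, p = 0.0455

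At that level, one unrecorded visit decides which side of 0.05 the result falls on. This shows sensitivity; it does not estimate how many visits would be missed.

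**The case against.** The strongest reply is that the wording is inconsistent, not that collection is absent. Much of this stands.

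- Sections 6.6.1 and Appendix 3 place the full question wording in the Manual of Procedures. That manual is not among the documents, and its questions may be wider than a schedule row label.
- The synopsis asks about visits without attribution and says that flu-like emergency visits are collected.
- Symptoms are reported daily, and adverse events daily and at every contact. COVID-19 symptoms are events of special interest with follow-up (7.8, 7.9), and documentation must be sought when an outside physician evaluates or treats an adverse event (7.3). These routes may surface some visits.
- Section 9.5.2 already excludes test-negative admissions, so part of what the endpoint wording admits is removed at analysis.

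A reader might therefore infer too much in three ways. One inference is that unattributed visits are never asked for, or that the endpoint cannot be assembled; the points above do not allow that. Another is that only the need for a visit is recorded, because Table 4 uses that word; Section 6.6.2 asks about visits that may have taken place. A third is that a percentage loss can be stated by assuming what share of visits participants attribute to COVID-19. Any such figure only restates the assumption, and it mixes the endpoint that includes all flu-like visits with the one restricted to test-positive participants.

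What the reply does not remove is that both operational items in the protocol are narrower than the endpoint, and that the general text in Section 6.6 leads back to one of them.

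**Conclusion.** The mismatch is real and is confined mainly to ER/ED visits without admission that the participant does not attribute to COVID-19. Their capture is not assured by the protocol as written. The clearest loss would be a visit that precedes a positive test, since Section 9.5.2 counts it. Admissions are not affected in the same way, because they are reported as SAEs.

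The number of visits missed cannot be computed from the documents. The case for acting rests on sparseness: about 12 infections are expected, and under a test-positive reading the endpoint is a subset of them. That reading is itself an assumption, because Section 9.5.2 does not say how test-negative or untested ER/ED visits are treated. The conclusion also assumes that the manual's questions follow the Table 4 and Section 6.6.2 wording; if they are already wider, what remains is to align the protocol text. For a secondary endpoint with a cheap repair, this should be corrected, but it does not bear on the primary analysis.

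**What to change.** 1. Reword the Table 4 row and the Section 6.6.2 contact item to record every hospitalisation or ER/ED visit since the last contact, whatever the cause, with date, main reason, whether a COVID-19 test was done, and its result. Check that the electronic and paper items in the Manual of Procedures match.
2. Derive the endpoint from those fields by a pre-specified rule applied blind to treatment, not from the participant's attribution.
3. Reconcile Sections 2.2 and 3.1 with Section 9.5.2. State whether flu-like visits count without a positive test, and in particular whether test-negative or untested ER/ED visits are events.

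The cost is one reworded row, one reworded contact item and the matching questionnaire item, plus some unrelated visits to record and filter out. Visits not recorded during the study may be hard to recover afterwards.
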